During the randomized vitamin E treatment phase, patients will be continue to be seen by the nutritionist every 8 weeks for individual follow-up visits and to reinforce components covered during the initial 12 week lifestyle intervention. During the extended treatment phase, the patients will be seen by the nutritionist every 12 weeks. Patients will complete the 3-day food intake diary and IPAQ every 24 weeks during the randomized treatment and extended treatment phases. The data obtained from these diaries and questionnaires will be used to ensure that differences in outcomes observed between the different vitamin E groups are not due to differences in adherence to lifestyle changes. Although part of the effect of treatment may be due to lifestyle intervention, it should affect all treatment groups in a similar manner and the effect of vitamin E will be deduced from the dose response.

Detailed in-patient assessment

At the beginning of the randomized-dose treatment phase, patients will be admitted to the Clinical center for a detailed histological, physiological and biochemical analysis, including:

- 1. History and physical examination: including vital signs, weight and anthropomorphic measurements.
- 2. Fasting blood tests: chem-20, GGT, CBC, PT, PTT, serum insulin, c-peptide, lipid panel, apolipoproteins, total free fatty acids, hemoglobin A1c, alpha-fetoprotein, ferritin, iron, transferrin saturation, immunoglobulins, TSH, C-reactive protein, PSA and vitamin E levels
- 3. Research blood: 10 ml of serum will be separated from collected blood and stored in 2 separate aliquots in -80°C for determining serum levels of hormones, cytokines and adipokines, injury markers (such as CK-18 fragments), and for archival storage. 10 ml of plasma will be separated from collected blood and stored at -80°C for analysis of oxidative stress measures.
- 4. NKT and NK cell analysis: 40 ml of blood will be drawn for analysis of NKT and NK cell phenotype and effector function. Additional 8 ml of serum tube (8 ml) will be used to provide autologous serum for in vitro functional assays. The frequency of performing these assays is detailed in table 1.
- 5. Urine tests: urinalysis, pregnancy test (for women of child-bearing potential) and 24-hour urine collection for creatinine clearance and protein and uric acid

excretion. A 5 ml urine sample will be stored at -80°C for oxidative stress measurements.

6. Imaging:

- a. Magnetic resonance imaging (MRI):

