⁵ NK/NKT cell analyses – On Run-in phase, first admission and week 144 will be drawn for all patients. On weeks 4 and 24 these will be performed only on the 200 IU/d and 800 IU/d arms (total volume 48 ml). On week 144 only 30 ml will be obtained. Will not be performed if Hb < 10 g/dL.

⁶ FSIVGTT – total blood volume drawn 120-150 ml. Will not be performed if Hb < 10 g/dL.

⁷ Possible lowering of vitamin E dose based on week 48 results (see Figure 4).

Analysis of the study

End points

Primary end points

There are two primary clinical end points in the study. The primary biochemical response is defined in a binary manner as an end-of-treatment AST <=32 or ALT <=35 U/L. The selection of these cut-off values is based on a pilot analysis by us that examined in an unbiased manner several rules for biochemical response and found this to be the one most strongly associated with histological response to treatment, irrespective of treatment modality³¹. We will also analyze the absolute change in ALT and AST from pre-treatment to end-of treatment as continuous parameters of the effect of treatment on liver enzymes. Patients who at the time of starting vitamin E treatment have normal liver enzymes will be excluded from this analysis. The primary physiological response is the absolute change in liver fat content as determined by comparing the ¹H-MRS results from pre-treatment to end of treatment.

Secondary end points

Secondary end points include: absolute and percent decrease in liver enzymes, decrease in GGT levels, percent reduction in liver fat.

A secondary analysis will analyze the effect of the lifestyle modification by comparing the end points between enrollment and the end of the lifestyle modification phase. Another analysis will determine the effect of increasing the dose of vitamin E by comparing the end points between the end of the randomized phase (week 24) to weeks 24 and 144 of the extended phase.

The kinetics of response will be determined by analyzing sequential ALT and AST measurements. Current data suggest biphasic response pattern to vitamin E and mathematical modeling will be applied to the results and will be compared between doses. Similar modeling will be applied to changes in liver fat content by ¹H-MRS.

Basic scientific end points

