Gene expression in liver and adipose tissue will be analyzed using microarray and quantitative PCR (qPCR) of tissue samples. Treatment-induced changes or comparisons between groups of patient (i.e. comparison of baseline expression between responders and non-responders) will be expressed as fold-induction.

NK and NKT cell changes in the serum and liver tissue will be analyzed using phenotyping and functional assays.

Oxidative stress will be measured in the serum, urine, liver and adipose tissue using TBARS assay, F₂-isoprostanes, 9-HODE, 13-HODE, SOD activity or similar measures. In women of child-bearing age, the phase of the menstrual cycle will be recorded on extended visits, as F₂-isoprostane levels can be affected by it.

Statistical analyses

Parameters of response to treatment will be analyzed by matched-pair comparison between pre-treatment and end of treatment values. Student's t-test will be used for values that are distributed normally while Wilcoxon's sign-ranked test will be used for non-parametric values. Categorical comparisons will be performed using X^2 or Fisher's exact test, as appropriate. The Cochran-Armitage test for trend will be used to test for a dose effect on the primary clinical end points.

To determine the effect of genetic variants, genotype-based analyses will be preferred to allelic analyses, with an additive model used primarily, unless other (dominant or recessive) models seem more appropriate. Linear or ordinal logistic regression will be used.

All analyses will be done with and without stratification for the presence of diabetes mellitus.

An $\alpha \le 0.05$ will be used to determine statistical significance.

Sample size calculation

The main goal of the study is to understand and characterize the mechanism of response to vitamin E. An important goal of the study is to simultaneously collect liver and adipose tissue to determine the site of action of the vitamin E and the relative contribution of each tissue to the disease. For most of the planned end points, including changes in liver fat content by ¹H-MRS and the basic scientific end points, there is not enough pre-existing data to allow for accurate sample size calculation.

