For the comparison of effectiveness between different doses of vitamin E (primary aim 1), the primary biochemical end point will be used. We assume a response rate of 45% with the 800 IU/d dose (similar to that seen at the PIVENS trial), a 10% response rate to the 200 mg/d dose and a 20% response to the 400 mg/d dose. Under these assumptions, a sample size of 25 patients per group will give a power of 80% to detect a linear trend with statistical significance of 5% (Cochran-Armitage test). To account for possible drop-out and loss to follow-up, we are aiming to recruit 30 patients per group or an overall of 90 patients in the study.

As the sample size calculation is limited by the absence of published data, we will re-assess our calculations after 10 patients have been enrolled in each arm, and again after 20 have been enrolled

Human subject protections

Rationale for subject selection

The study is designed to enroll patients with NAFLD that can be potentially benefit from treatment. Currently, there are no reliable non-invasive markers that accurately distinguish NASH from steatosis only, although the latter seems to carry a more favorable prognosis. For patients with steatosis only, it is unclear whether treatment can improve their disease and prevent progression to NASH. In most clinical trials with histological end points, patients with steatosis only were excluded as they cannot show significant histological

improvement. In this study, with a primarily scientific outcome, we are interested in studying the effect of vitamin E on these patients as well and we consider the intervention to be low-risk enough to allow us to recruit all patients with NAFLD.

The exclusion criteria for the study are mainly geared towards limiting enrollment to patients for whom treatment is considered safe and that have no confounders that would limit the analysis of the results. There are no limitations based on race or ethnicity. However, we anticipate that very few patients of African ancestry will be enrolled, because of the scarcity of NAFLD in these patients and their apparent "protection" from liver fat accumulation.

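### The continuous ALT and AST changes get only a before/after test; no dose-trend test is named for them, although the trial has no control arm and reads the effect from dose

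*Combined protocol and SAP*

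**What the plan says.** The Primary end points section makes enzyme response a yes/no outcome: "The primary biochemical response is defined in a binary manner as an end-of-treatment AST <=32 or ALT <=35 U/L". The cut has a stated reason: a pilot analysis compared several rules and "found this to be the one most strongly associated with histological response to treatment". The same paragraph then adds: "We will also analyze the absolute change in ALT and AST from pre-treatment to end-of treatment as continuous parameters".

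The Statistical analyses section says: "Parameters of response to treatment will be analyzed by matched-pair comparison between pre-treatment and end of treatment values". It names the t-test or the Wilcoxon signed-rank test for this. For dose it says: "The Cochran-Armitage test for trend will be used to test for a dose effect on the primary clinical end points".

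The Sample size calculation section ties the dose question to the binary outcome: "For the comparison of effectiveness between different doses of vitamin E (primary aim 1), the primary biochemical end point will be used". With assumed response of 10%, 20% and 45% on 200, 400 and 800 IU/d, it states that "a sample size of 25 patients per group will give a power of 80% to detect a linear trend".

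Two design statements bear on this. The section on the absence of a control arm explains why there is no placebo group. The section on the run-in phase accepts that lifestyle change may contribute to the result, and says "the effect of vitamin E will be deduced from the dose response".

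**The concern.** Without a control arm, only a comparison between doses can separate vitamin E from lifestyle change, time and regression to the mean. A paired test within patients cannot do so, and it says nothing about which dose is best. Yet it is the only test the plan names for the continuous enzyme changes. Cochran-Armitage cannot fill the gap: the plan applies it to the primary clinical end points in the plural, but it cannot be run on a change in U/L.

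Primary aim 1 therefore rests on three proportions from about 25 patients each. The cut records which side of a line a patient ends on, not how far the enzymes fell. The measured values come from the same blood draws and could give dose ratios with confidence intervals. Leaving the method open also leaves the choice among raw, percent and log change until the data are seen; the plan already lists both absolute and percent decrease.

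**Working it through.** **Inputs from the plan.** Response 0.10, 0.20, 0.45; n = 25 per arm; significance level 5%. Sidedness, dose scores and continuity correction are not stated; I take two-sided.

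**Step 1: the plan's 80%.** Take scores 200, 400, 800, with deviations d = -266.67, -66.67, 333.33 and Σd² = 186,667.

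- Expected trend: nΣdp = 25 × 110 = 2,750.
- Null SD: √(25 × 0.25 × 0.75 × 186,667) = 935.4.
- SD under the alternative: √(25 × Σd²p(1-p)) = 930.2.
- Power, uncorrected: Φ[(2,750 - 1.96 × 935.4)/930.2] = Φ(0.985) = 0.838.
- Power with a continuity correction of 100 (half the smallest score gap): Φ[(2,650 - 1,833.4)/930.2] = Φ(0.878) = 0.810.

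An exact conditional test with scores 1, 2, 3 gives 0.797. Full enumeration of the uncorrected test gives 0.840-0.846. The plan's figure reproduces.

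**Step 2: a dose trend on the measured scale.** The documents give no SD, distribution or pre/post correlation for ALT or AST, so these are assumptions. Treat one log enzyme as normal with equal SD in each arm, and shift each arm so that 10%, 20% and 45% fall below the cut. The arm means then lie m = 1.282, 0.842 and 0.126 SD above the cut. With the pre-treatment value as covariate and pre/post correlation ρ, the noncentrality is

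λ = √n |Σdm| / [√Σd² √(1-ρ²)] = 5 × 355.97 / [432.05 √(1-ρ²)] = 4.12/√(1-ρ²).

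Power is about Φ(λ - 1.99):

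- ρ = 0: Φ(2.13) = 0.98.
- ρ = 0.3: λ = 4.32, power 0.99.
- ρ = 0.5: λ = 4.76, power 0.997.
- ρ = 0.7: λ = 5.77, power above 0.999.

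**Step 3: simulation of the candidate outcomes.** Assumptions: lognormal ALT, baseline median parameter 70-85 U/L, log SD 0.4-0.5, patients at or below 35 U/L excluded, 25 per arm, 20,000 trials per setting.

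| Analysis | ρ = 0.3 | ρ = 0.5 | ρ = 0.7 |
|---|---|---|---|
| Binary, Cochran-Armitage | 0.84-0.85 | 0.85 | 0.85 |
| Log ALT adjusted for log baseline | 0.99 | 0.996 | 1.00 |
| Log change | 0.94-0.96 | 0.99 | 1.00 |
| Raw absolute change | 0.57-0.74 | 0.68-0.85 | 0.83-0.96 |

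Raw absolute change, the parameter the plan names, is often weaker than the binary test.

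**Step 4: sensitivity, without baseline adjustment.**

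- Other shapes: logistic 0.97; t with 5 df about 0.945; skewed 0.82-0.83 or 0.995, depending on the direction of skew.
- The two-enzyme rule, with ALT-AST correlation 0.5-0.9: 0.96-0.98 using one enzyme, 0.985-0.991 using the mean of both.
- Only a subset responds: falls of 1.5, 2.0 and 2.5 SD in that subset give 0.93, 0.86 and 0.85, against 0.84-0.85 for the binary test. The gain is about 8, 2 and 0 points.

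**The case against.** The strongest reply is that the cut was chosen deliberately for its link to histology, that the trial meets its stated power, and that a phase IIa study aimed mainly at mechanism need not squeeze more from ALT. All of this stands. It supports keeping the binary response as the formal analysis. It gives no reason to leave the continuous parameters with only a paired test.

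Four stronger readings are tempting, and the documents do not support them.

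- A reader might infer that measured ALT and AST are never compared between doses. The Secondary end points section does plan kinetic modelling of serial ALT and AST, set against each other by dose. It names no model, parameter or test, and is not tied to primary aim 1.
- A reader might infer that the plan's response rates by themselves imply a loss of 10-14 points of power. That range comes from assuming a common shift in a symmetric outcome. The plan reasons elsewhere in responders and non-responders, for example in its week-48 rule, so the subset case with little or no gain is plausible.
- A reader might take the recomputed 84-85% as showing that 80% is wrong. The difference is the continuity correction or exact test.
- A reader might say that a fall in ALT from 150 to 40 U/L counts as failure. It does so only if AST also stays above 32, because either enzyme suffices.

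**Conclusion.** The gap is real and narrow: no dose-trend test is specified for the continuous ALT and AST changes, and the test that is specified cannot inform primary aim 1 in a trial without controls. Nothing is miscalculated.

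Under lognormal enzymes with a common shift and 25 per arm, a baseline-adjusted log-scale model has about 98-100% power for a dose trend, against about 84% for the binary test. The advantage belongs to that model, not to continuous data in general: raw absolute change ranges from about 57% to 96%. It also shrinks toward zero if dose works only through large falls in some patients.

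The analysed number could be below 25 per arm. Patients with normal enzymes at the start of vitamin E are left out of the enzyme analysis, and the increase from 25 to 30 is explained only by drop-out and loss to follow-up. The documents give no estimate of how many this removes.

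Because the added model would be supporting, its benefit is a better dose estimate. It does not raise the formal power for aim 1.

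**What to change.** Keep the binary response and its Cochran-Armitage test as the formal, sized analysis. In the Statistical analyses section:

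1. Add, as the supporting dose analysis for primary aim 1, a linear model of log week-24 ALT on randomized dose (trend contrast), with the log pre-treatment ALT as covariate. Do the same for AST.
2. Report ratios of geometric means for 400 v 200 and 800 v 200 IU/d, with 95% confidence intervals.
3. State that the before/after comparisons are descriptive.

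This takes two or three sentences and one model per enzyme, with no new data, visits or patients. The downside is one more pre-specified analysis. Labelling it as supporting keeps it from becoming a second route to a claim of success.

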We propose a phase IIa study to determine the optimal dose of vitamin E and its mechanism and site of action. In this study we aim to enroll up to 90 patients with NAFLD. Initially, all patients will undergo 12 weeks of intensive lifestyle modification. Following that, all patients will be randomized to treatment with 3 different doses of natural vitamin E (rrr- α -tocopherol at 200, 400 or 800 IU/d) for 24 weeks. The primary end points for efficacy are normalization of liver enzymes and reduction in liver fat contents by magnetic resonance spectroscopy. Patients will undergo liver and adipose tissue biopsies before vitamin E treatment and after 4 weeks of therapy, and the biopsy samples will be used to measure changes in gene expression and markers of oxidative stress. This will be coupled with extensive phenotyping before and after treatment using serological, radiological and dynamic endocrine testing and is aimed at finding the dose-response characteristics of vitamin E in NAFLD, and allowing us to understand the mechanism of its action.

After 24 weeks of randomized treatment, all patients will be switched to a dose of 800 IU/ml and will continue treatment for up to 30 months, at the end of which another liver biopsy will be performed. From this phase we will assess the effects of dose increase of vitamin E on liver enzymes and fat content, and will determine the effect of long-term treatment on histological outcome.

Table of Contents

Précis	3
Table of Contents	4
Introduction	6
Non-alcoholic fatty liver disease	6
Vitamin E	7
Vitamin E for NAFLD	8
Aims	10
Primary Aims:	10
Secondary aims:	10
Study design and methods	11
Overall design (Figure 3)	11
Initial screening and enrollment	12
Run-in phase and lifestyle intervention	12
Detailed in-patient assessment	14
Vitamin E Treatment	15
Extended Treatment Phase	16
Details of procedures	18
Adipose Tissue Biopsy	18
Liver Biopsy	18
Magnetic Resonance Spectroscopy	19
Justification for study design	19
Run-in phase	19
Liver biopsies	20
Absence of a control arm	21
Duration of treatment	21
Inclusion and exclusion criteria	21
Inclusion	21
Exclusion criteria	
Monitoring subjects and criteria for withdrawal of subject from the study	
Analysis of the study	
End points	27

Vitamin E for Non-Alcoholic Fatty Liver

Primary end points	27
Secondary end points	27
Basic scientific end points	27
Statistical analyses	28
Sample size calculation	28
Human subject protections	28
Rationale for subject selection	28

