Experiments will be performed on an MRI scanner using TIM phased-array coils. B_0 shim parameters are optimized with a breath hold B_0 mapping method²⁷. Navigator gated T_2 weighted (T2w) and breath-hold T_1 weighted (T1w) images in coronal and axial orientations will be used to prescribe a 20x20x20 mm³ spectroscopy volume in an area with high signal to noise ratio, free of obvious fatty structures or blood vessels. After additional manual shimming, and optimization of transmit power and WS RF level 32 signals will be averaged with a minimum repetition time (TR) of 3s and 35 ms echo time (TE) with WET water suppression (WS) followed by 4 signals averaged with WS RF power set to zero. Spectral data will be fitted with AMARES²⁸ using a model of four resonances for the lipid signals on the WS spectra. Additionally, the apparent T_2 's of the summed lipid CH_2 and CH_3 resonances lipid and the T_2 of water will be measured with five quick expiration breath hold non-WS spectra averaging two signals each at TR 3s and TE 24, 36, 48, 96 and 144 ms. These T_2 values will be used to correct the water and total lipid signals for signal decay in the 35 ms echo delay. Fat fraction will be then calculated as from the T2 corrected signals S_{water} and S_{lipid} as: fat fraction = $S_{lipid}/(S_{water}+S_{lipid})$.

Justification for study design

Run-in phase

To date, most trials in NAFLD enrolled patients based on the results of a pre-enrollment liver biopsy, which was not necessarily performed immediately prior to enrollment. However, in clinical practice a decrease in liver enzymes is often seen in the first few months after a patient is given a diagnosis of NAFLD, probably reflecting a serious attempt at lifestyle modification. Similar effects were noted in placebo-treated patients^{7, 29}. This is especially important in studies with a histological end-point, in which the true baseline status may thus be different than the one suggested by a "distant" enrollment biopsy. Furthermore, it may not be justified to suggest pharmacological interventions to patients who are controlling their disease adequately with dietary modification and physical activity.

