There is no clear accepted duration of treatment for NASH and similar to other metabolic conditions like diabetes or hypertension, treatment is probably required for life. The kinetics of biochemical response in the previous vitamin E trials (figure 2) show near-plateauing at week 24, and suggest little incremental benefit will be achieved by extending treatment beyond that.

Inclusion and exclusion criteria

Inclusion

- 1. Clinical suspicion of NAFLD, defined by the presence of at least two of the following criteria:
 - a. Suggestion of liver fat by an imaging study (ultrasound, CT scan, MRI or MR spectroscopy) performed in the 6 months prior to enrollment.
 - b. Elevated aminotransferase levels (ALT > 31 U/L for men or > 19 U/L for women, or AST > 30 U/L) on at least two occasions in the 6 months preceding enrollment.
 - c. Presence of the metabolic syndrome, defined according to the modified AHA/NCEP criteria³⁰ as the presence of at least three of:
 - i. Abdominal obesity, defined as waist circumference > 102 cm for men or > 88 cm for women
 - ii. Elevated triglycerides (> 150 mg/dL) or the use of medication to lower triglycerides
 - iii. Reduced HDL cholesterol (< 40 mg/DL for men or < 50 mg/dL for women)
 - iv. Elevated blood pressure (> 135/80 mmHg) or use of medication for hypertension
 - v. Elevated fasting glucose levels (> 100 mg/dL) or use of anti-diabetic medication

For the purpose of inclusion, the presence of overt diabetes mellitus type 2 will be considered equivalent to the presence of the metabolic syndrome, even if the other criteria are absent.

- 2. Estimated average alcohol consumption < 30 g/d for men or < 20 g/d for women in the 6 months prior to enrollment and no binge-drinking behavior.
- 3. Age > 18 years at enrollment
- 4. Willingness to participate in the study

Exclusion criteria

- 1. Chronic infection with hepatitis C virus (HCV) or hepatitis B virus (HBV). Patients who were treated successfully for HCV and achieved sustained virological response can be eligible for enrollment > 18 months after treatment cessation. Patients who are inactive carriers of HBV (HBV DNA < 1000 copies/mL, HBeAg negative, Anti HDV negative) for at least 12 months prior to enrollment are also eligible. Patients receiving antiviral therapy are ineligible.
- 2. Concomitant liver disease such as autoimmune hepatitis, primary biliary cirrhosis, primary sclerosing cholangitis, Wilson's disease, alpha-1 antitrypsin deficiency.

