Patients with hemoglobin < 10 g/dL will not undergo the FSIVGTT test and/or collection of blood for NK/NKT cells. Patients with hemoglobin < 10 g/dL will not undergo the first (baseline) liver biopsy. That biopsy may be deferred for up to 4 weeks if the anemia can be treated sufficiently by that time. Patients who cannot undergo the baseline liver biopsy will be withdrawn from the study. Patients with hemoglobin < 10 g/dL will not undergo the second or third liver biopsy; these biopsies will not be deferred but the patients may continue on the study.

Vitamin E for Non-Alcoholic Fatty Liver

Table 1 – Monitoring and investigation schedule

Phase	Visit week	Vit E dose	Nurse ¹	MD	Nutritionist ²	Routine labs ³	Extended labs ⁴	NK/NKT cell studies ⁵	Liver & Adipose Tissue Biopsy	FSIVGTT ⁶	Imaging	Breath Test	Questionaires
Enrollment	(-4) – (-1)		+	+		+							DHQ II, IPAQ, 3-day food
Run-in	0		+		++	+	+	+			MRS, MRI		Symptom, quality of life
	2				++, +								
	4		+		+	+							
	6				+								
	8		+		+	+							
	10				+								
Admission	12		+	+	++	+	+	+	+	+	MRS, MRI, DEXA	+	3-day food, IPAQ, symptom, quality of life
Randomized Rx	0 (1-2 wk later)	200/400/800	+	+		+							
	1	200/400/800	+			+							
	2	200/400/800	+			+							
	3	200/400/800	+			+							
2 nd Admission	4	200/400/800	+			+	+	+	+	+	MRS		
	8	200/400/800	+	+	++	+							
	12	200/400/800	+			+	+						symptom
	16	200/400/800	+	+	++	+							
	20	200/400/800	+			+							
3rd Admission	24	800	+	+	++	+	+	+		+	MRS, MRI, DEXA	+	3-day food, IPAQ, symptom, quality of life
Extended Rx	36	800	+	+	++	+							
	48	800 (or lower ⁷)	+	+	++	+	+				MRS		3-day food, IPAQ, symptom, quality of life
	60-132 (q12 wks)	800 (or lower ⁷)	+	+	++	+	+ (q24 wks)						3-day food, IPAQ, symptom, quality of life (q 24 wks)

Vitamin E for Non-Alcoholic Fatty Liver

Exit Admission	144	Stop	+	+	++	+	+	+5	+	+	MRS, MRI, DEXA,	+	3-day food, IPAQ, symptom, quality of life

¹ Nursing visit – includes vital signs, weight, list of current study and non-study medications and nursing assessment

² Nutrition visit - + marks group session, ++ marks individual session

³ Routine labs – complete blood count, Chem-20, serum insulin, c-peptide, free fatty acids, lipid panel, vitamin E level, research blood (total volume 31.5 ml)

⁴ Extended labs – GGT, PT, PTT, HbA1c, CRP, Thyroid panel, apolipoproteins, ferritin, iron, transferrin saturation, immunoglobulins, PSA, research plasma (total volume 52.5 ml with Routine labs), urinalysis

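### The baseline exclusion for the biochemical end point is not tied to the response rule, so patients who already meet that rule may stay in the dose-trend test

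*Combined protocol and SAP*

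**What the plan says.** The section Primary end points (under Analysis of the study) makes biochemical response a state at the end of treatment, "defined in a binary manner as an end-of-treatment AST <=32 or ALT <=35 U/L". No change from baseline is required. The next step is a continuous analysis: "We will also analyze the absolute change in ALT and AST from pre-treatment to end-of treatment". The block then closes with the exclusion: "Patients who at the time of starting vitamin E treatment have normal liver enzymes will be excluded from this analysis".

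Other parts of the document bear on what normal means here:

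- The Précis describes the end point as normalization: "The primary end points for efficacy are normalization of liver enzymes". This points to the response limits.
- Inclusion criterion 1b uses different limits: "Elevated aminotransferase levels (ALT > 31 U/L for men or > 19 U/L for women, or AST > 30 U/L".
- The week-48 rule in Extended Treatment Phase refers to normal ALT or normal AST and gives no limits.

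The section Sample size calculation assumes response rates of 10%, 20% and 45% from lowest to highest dose. It states 80% power for a Cochran-Armitage trend test with 25 per group, and raises recruitment to 30 per group for drop-out and loss to follow-up. It plans to re-assess the calculation after 10 and again after 20 patients per arm.

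**The concern.** The response rule needs only one enzyme at or below its limit. The exclusion, read plainly, may need both to be normal. The two are not complements, so a patient can escape the exclusion and already satisfy the end point before the first capsule. If that patient stays as he or she is, the analysis counts a response at whichever dose was allocated.

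Such patients are foreseeable. Criterion 1 ("Clinical suspicion of NAFLD, defined by the presence of at least" two of three findings) admits a patient on imaging plus metabolic syndrome with no raised enzymes. The justification for the run-in notes that "a decrease in liver enzymes is often seen in the first few months" after diagnosis, and 12 weeks of lifestyle change come before treatment.

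At stake is power for primary aim 1, the only comparison the study is sized for. Allocation is randomised, so neither retaining nor removing these patients favours a dose.

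**Working it through.** **Step 1: who stays in under each reading.**

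| Reading of normal | Patient at baseline | Excluded? | Already meets AST <=32 or ALT <=35? |
|---|---|---|---|
| Both enzymes normal | ALT 80, AST 30 | No | Yes (AST) |
| Entry limits of criterion 1b | Woman, ALT 28, AST 31 | No (28 > 19; 31 > 30) | Yes (both) |
| The response rule itself | Either of the above | Yes | Yes |

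Only the third reading removes every patient who already meets the rule.

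**Step 2: reproduce the plan's figure.** Inputs from Sample size calculation: 10/20/45%, 25 per group, 5% level. All outcomes of three binomials were enumerated. A two-sided conditional exact Cochran-Armitage test with equally spaced scores gives 79.7%, which matches the stated 80%. The plan names neither the test version nor the scores. The asymptotic version gives 84.0%.

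**Step 3: effect of the wording.** Let b be the share of randomised patients who already meet the rule. The documents do not give b, so it is an assumption. Assume also that 10/20/45% applies to the others and that retained patients keep responding.

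- All retained: rate = b + (1 - b)p. For b = 20%, 0.2 + 0.8 x (0.10, 0.20, 0.45) = 28/36/56%.
- All removed: rates stay 10/20/45% and n falls. For b = 20%, 25 x 0.8 = 20 per group.
- Half retained, half removed, b = 20%: 25 x 0.9 = 22.5 per group remain, of whom 2.5/22.5 = 11.1% are retained early responders. Rates are 20/28.9/51.1%. Power is 55.5% at n = 22 and 57.9% at n = 23.

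Exact power, equal scores:

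| b | All retained, n = 25 | All retained, n = 30 | All removed, from 25 | All removed, from 30 |
|---|---|---|---|---|
| 5% | 71% | 79% | 76-77% (n 23-24) | 85-86% (n 28-29) |
| 10% | 62% | 72% | 74-76% (n 22-23) | 84% (n 27) |
| 20% | 46% | 56% | 70% (n 20) | 77% (n 24) |
| 30% | 35% | 40% | 60-64% (n 17-18) | 71% (n 21) |

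The columns from 25 correspond to the planned loss of 5/30 = 17%; those from 30 assume no drop-out. The half-and-half case from 30 (n = 27) gives 63.6%.

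**Step 4: sensitivity.**

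- If only 80% of the retained patients still respond, b = 20% and n = 25 gives 48% instead of 46%.
- With the asymptotic test, b = 20% from 25 gives 56% retained and 76% removed, so the order is the same.
- If 10/20/45% already includes patients who met the rule at the start and keep responding, b cannot exceed the lowest rate, 10%. Retaining them then gives the planned 79.7%. Removing them changes the rates to (p - b)/(1 - b): 5.3/15.8/42.1% at b = 5% (power 87-88% at n 23-24) and 0/11.1/38.9% at b = 10% (97-98% at n 22-23).

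**The case against.** The plan does have a safeguard, and the Précis supports reading normal as the response rule. On that reading nothing is diluted. The assumed 10% at the lowest dose points the same way: it cannot be an all-analysed rate if 20% or 30% of patients are persistent responders from the start, so the calculation seems to presuppose their removal. The share is unknown and may be small. At 5% retained with no drop-out, power is 79%, practically no shortfall. The planned re-assessments would also come at a time when the share could be seen. All of this stands, and it rules out treating any power figure above as the expected loss.

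A reader might also infer that the exclusion covers only the continuous ALT/AST change, since that sentence comes just before it, so that every early responder enters the trend test. The wording permits this, but it is the least natural reading. The exclusion closes the whole biochemical block, and it would make little sense to drop such patients from a change score yet count them as responders in a normalization end point. The all-retained figures are therefore an upper bound on the dilution for a given share. Under the both-enzymes reading, patients with both enzymes normal leave and only discordant ones stay, as in the half-and-half case.

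The objection does not close the gap between a one-enzyme response rule and an exclusion that may need both enzymes to be normal. Nor do the re-assessments have a stated rule or mention this exclusion.

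**Conclusion.** The concern holds as a mismatch between the exclusion and the response rule. Followed literally, the plan can keep patients who already meet the end point and count them as responders at every dose. If normal is instead taken to mean the response rule, the evaluable number falls, and the step from 25 to 30 per group does not name that loss.

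The documents do not fix the size. On the stated assumptions, a 20% share and 25 per group give about 46% (all retained), 56% (half retained) or 70% (all removed). When the planned rates describe patients not meeting the rule at the start, removing by the response rule keeps more power than retaining at every share tabulated. When those rates already include such patients, retaining costs nothing against the plan. The documents support neither a claim that power is in fact below 80% nor a claim of bias towards any dose. This should be fixed because the correction is cheap and affects the primary comparison.

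**What to change.** For the binary end point, replace the normal-enzyme condition with: patients who already meet the response definition (AST <=32 or ALT <=35 U/L) at randomised week 0 are excluded. Table 1 already marks routine labs at that visit, and footnote 3 lists them as "complete blood count, Chem-20, serum insulin, c-peptide, free fatty acids, lipid panel, vitamin E level, research blood", so the values will exist. Keep these patients in the liver-fat analysis.

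Keep 90 recruited. State that the 80% refers to 25 evaluable patients per group after this exclusion as well as drop-out. Show power over a range of excluded shares, labelled illustrative: for 10/20/30% excluded, 74-76/70/60-64% after the planned 17% loss and 84/77/71% with no drop-out. While editing, it would help to say whether the continuous analysis keeps its own exclusion and with what limits, and to name the test version and scores; these are missing details rather than part of the fault.

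The cost is a reworded exclusion and a restated power, with no extra patients, visits or tests. The downside is a smaller binary analysis set and a stated power that may fall below 80%. The change does not recover power lost to exclusion; it prevents already-responding patients from diluting the trend and makes the remaining power visible.
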